800 An appointment for Visit 3 will be scheduled.

801 **5.2.2. Questionnaires**

802 Participants will be sent the following questionnaires on the final week of the Run-in Period and
803 will be asked to complete them within 1 week:

- 804 • T1-Diabetes Distress Scale
- 805 • Hypoglycemia Fear Survey

CLINICAL PROTOCOL

- 806 • Hyperglycemia Avoidance Scale

807 **5.3. Visit 3 – Eligibility Assessment, Randomization and Training**

808 The participant may complete this visit via web conferencing and/or at the study site.

809 **5.3.1. Eligibility Assessment**

810 The CGM and insulin data will be reviewed to assess whether the subject has used the DiAs
811 system in SAM on at least 11 out of 14 days for CGM users or 22 out of 28 days for non-CGM
812 users. Subjects who are unable to meet the CGM and DiAs compliance requirement will be
813 withdrawn from the study, unless the investigator believes that there were extenuating
814 circumstances that prevented successful completion. In such cases, the investigator may ask the
815 participant to repeat this eligibility assessment.

816 **5.3.2. Adverse Event Assessment**

817 The participant will be asked about any of adverse events, adverse device effects, and device
818 issues since the last visit. The participant will also be asked if there were any low BGs <54 mg/dL,
819 high BGs >300 mg/dL, or ketones ≥ 3.0 mmol/L since the last visit. Participants will be encouraged
820 to contact the study team between visits as needed (i.e. report adverse events in real-time).

821 **Chapter 6 Study Procedures - Escalation**

822 **6.1.1. Randomization to Escalation**

823 Eligible subjects will be randomized to therapy escalation (SAM→PF→DSS).

824 A baseline Hemoglobin A1C will be collected. The participant will receive a mode change for
825 Phase 1 according to the randomization scheme.

826 **6.2. Sensor Augmented Mode**

827 Participants randomized to escalation will have any questions answered about continuing use of
828 the DiAs system in SAM.

829 **6.2.1. SAM EMA Surveys**

830 Over the course of 2-3 days every two weeks of Phase 2, the participant will be asked to complete
831 a “Daily Diary” with 3-5 entries of 3-4 questions each day, for a minimum total of 48 entries per
832 participant during each Phase.

833 **6.2.2. Phase 1 Initiation Questionnaires**

834 Participants randomized to escalation will complete the following questionnaires:

- 835 • Pittsburgh Sleep Quality Index

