1394 such as a bit of liquid soap with warm water will be used. A soft towel will be used to dry the
1395 pump.

1396 Equipment that touches intact skin will be cleaned with ethyl or isopropyl alcohol (70-90%),
1397 quaternary ammonium germicidal detergent (i.e. Cavicide, EPA number 46781) or household
1398 bleach. The contact time on the surface depends on the method used to clean the equipment.
1399 Cavicide requires three minutes on the surface of the equipment. Clorox Germicidal Bleach Wipes
1400 require two minutes on the equipment. The surface should remain wet (i.e. slightly damp) with
1401 the disinfectant to be considered effective though not wet enough to leave drops of liquid.

1402 In the event a manufacturer update for cleaning procedures of their device, the study team will
1403 adhere to the most current recommendations.

1404 **Chapter 12 Adverse Events, Device Issues, and Stopping Rules**

1405 The protocol is considered a significant risk device study due to the fact that the closed loop
1406 system is experimental. Therefore, an investigational device exemption (IDE) from the U.S. Food
1407 and Drug Administration (FDA) is required to conduct the study.

1408 **12.1. Definitions**

1409 **12.1.1. Adverse Events (AE)**

1410 A reportable adverse event includes any untoward medical occurrence that meets one of the
1411 following criteria:

- 1412 • A Serious Adverse Event as defined in section 12.1.2
- 1413 • An Adverse Device Effect as defined in section 12.1.4, unless excluded from reporting in
1414 section 12.8
- 1415 • An Adverse Event as defined in section 12.1.4 occurring in association with a study
1416 procedure
- 1417 • An AE as defined in section 12.1.1 which leads to discontinuation of a study device for 2
1418 or more hours
- 1419 • Hypoglycemia meeting the definition of severe hypoglycemia as defined in section 12.3.1
- 1420 • Diabetic ketoacidosis (DKA) as defined in section 12.3.2 or in the absence of DKA, a
1421 hyperglycemic or ketosis event meeting the criteria defined below

1422 Hypoglycemia and hyperglycemia not meeting the criteria below will not be recorded as adverse
1423 events unless associated with an Adverse Device Effect. Skin reactions from sensor placement
1424 are only reportable if severe and/or required treatment.

1425 **12.1.2. Serious Adverse Event (SAE)**

1426 Any untoward medical occurrence that:

- 1427 • Results in death.

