1457 participant, the investigator, or the study site staff. As a result of deviations, corrective actions
1458 may be developed by the site and implemented as appropriate. Major deviations will be reported
1459 to the IRB-HSR within 7 calendar days of when the study team becomes aware of the event.

1460 **12.3. Reportable Events**

1461 **12.3.1. Hypoglycemia Event**

1462 Hypoglycemia not associated with an Adverse Device Effect is only reportable as an adverse event
1463 when the following definition for severe hypoglycemia is met:

CLINICAL PROTOCOL

- 1464 • The event required assistance of another person due to altered consciousness, and
1465 required another person to actively administer carbohydrate, glucagon, or other
1466 resuscitative actions;
- 1467 • Impaired cognitively to the point that he/she was unable to treat himself/herself, was
1468 unable to verbalize his/ her needs, was incoherent, disoriented, and/or combative, or
1469 experienced seizure or coma. These episodes may be associated with sufficient
1470 neuroglycopenia to induce seizure or coma;
- 1471 • If plasma glucose measurements are not available during such an event, neurological
1472 recovery attributable to the restoration of plasma glucose to normal is considered
1473 sufficient evidence that the event was induced by a low plasma glucose concentration.

1474 **12.3.2. Hyperglycemia Events/Diabetes Ketoacidosis**

1475 Hyperglycemia not associated with an Adverse Device Effect is only reportable as an adverse
1476 event when one of the following four criteria is met.

1477 The event involved DKA, as defined by the Diabetes Control and Complications Trial (DCCT) and
1478 described below:

- 1479 • Evaluation or treatment was obtained at a health care provider facility for an acute event
1480 involving hyperglycemia or ketosis
- 1481 • Blood ketone level ≥ 1.5 mmol/L and communication occurred with a health care provider
1482 at the time of the event
- 1483 • Blood ketone level ≥ 3.0 mmol/L, even if there was no communication with a health care
1484 provider
- 1485 • Hyperglycemic events are classified as DKA if the following are present:
 - 1486 ○ Symptoms such as polyuria, polydipsia, nausea, or vomiting;
 - 1487 ○ Serum ketones ≥ 1.5 mmol/L or large/moderate urine ketones;
 - 1488 ○ Treatment provided in a health care facility

1489 All reportable Adverse Events—whether volunteered by the participant, discovered by study

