1490 personnel during questioning, or detected through physical examination, laboratory test, or
1491 other means—will be reported on an adverse event form online. Adverse events will be
1492 presented to the DSMB in accumulated manner during each meeting.

1493 **12.4. Relationship of Adverse Event to Study Device**

1494 The study investigator will assess the relationship of any adverse event to be related or unrelated
1495 by determining if there is a reasonable possibility that the adverse event may have been caused
1496 by the study device.

CLINICAL PROTOCOL

1497 To ensure consistency of adverse event causality assessments, investigators should apply the
1498 following general guideline when determining whether an adverse event is related:

- 1499 • There is a plausible temporal relationship between the onset of the adverse event and
1500 the study intervention, and the adverse event cannot be readily explained by the
1501 participant's clinical state, intercurrent illness, or concomitant therapies; and/or the
1502 adverse event follows a known pattern of response to the study intervention; and/or the
1503 adverse event abates or resolves upon discontinuation of the study intervention or dose
1504 reduction and, if applicable, reappears upon re-challenge.
- 1505 • Evidence exists that the adverse event has an etiology other than the study intervention
1506 (e.g., preexisting medical condition, underlying disease, intercurrent illness, or
1507 concomitant medication); and/or the adverse event has no plausible temporal
1508 relationship to study intervention.

1509 **12.5. Intensity of Adverse Event**

1510 The intensity of an adverse event will be rated on a three point scale: (1) mild, (2) moderate, or
1511 (3) severe. It is emphasized that the term severe is a measure of intensity: thus, a severe adverse
1512 event is not necessarily serious. For example, itching for several days may be rated as severe, but
1513 may not be clinically serious.

- 1514 • **MILD:** Usually transient, requires no special treatment, and does not interfere with the
1515 participant's daily activities.
- 1516 • **MODERATE:** Usually causes a low level of inconvenience or concern to the participant and
1517 may interfere with daily activities, but is usually ameliorated by simple therapeutic
1518 measures.
- 1519 • **SEVERE:** Interrupts a participant's usual daily activities and generally requires systemic
1520 drug therapy or other treatment.

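### Visit questions ask about ketones only from 3.0 mmol/L, while the protocol makes 1.5 mmol/L with provider contact reportable

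*Combined protocol and SAP*

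**What the plan says.** The adverse event assessment in 5.3.2 (Visit 3) begins with an open question about adverse events, adverse device effects and device issues. It then asks about glucose below 54 mg/dL and about "high BGs >300 mg/dL, or ketones ≥ 3.0 mmol/L since the last visit". Sections 6.4.3, 6.6.3 and 6.8.2 (escalation) and 7.4.3, 7.6.3 and 7.8.2 (de-escalation) use the same levels. The Visit 7 check-in (6.9 and 7.9) covers adverse events, device effects, device issues, and glucose below 60 or above 300 mg/dL. It does not mention ketones.

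Section 12.1.1 makes reportable, even without DKA, a "hyperglycemic or ketosis event meeting the criteria defined below". Section 12.3.2 requires only one of four criteria. Besides DKA itself, these are:

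- "Evaluation or treatment was obtained at a health care provider facility for an acute event" that involved hyperglycemia or ketosis;
- blood ketones of at least 1.5 "mmol/L and communication occurred with a health care provider" at the time of the event;
- blood ketones of at least 3.0 mmol/L, "even if there was no communication with a health care" provider.

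Reportable events may be volunteered, found by "personnel during questioning, or detected through physical examination, laboratory test, or" other means, and are "presented to the DSMB in accumulated manner during each meeting".

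**The concern.** The targeted question covers only one of the two ketone criteria. It asks for the level that is reportable on the number alone and omits the lower level that becomes reportable once a provider has been contacted. A participant is unlikely to know that a reading of 1.8 mmol/L plus a phone call crosses a reporting line, so without a prompt the event depends on the participant thinking to mention it.

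What is at stake is the completeness of the safety record. Section 10.1.6 names ketonemia as a risk, and 10.3 accepts that the dosing advice may make hyperglycemia more likely. Events that meet the protocol's own definition could be missing from what the DSMB reviews.

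**Working it through.** There is no stated figure to reproduce. The check compares each ketone prompt with the reporting criteria.

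| Place | Contact | Ketone level named |
|---|---|---|
| 5.3.2 | Visit 3, both sequences | 3.0 mmol/L or more |
| 6.4.3, 7.4.3 | Visit 4 | 3.0 mmol/L or more |
| 6.6.3, 7.6.3 | Visit 5 | 3.0 mmol/L or more |
| 6.8.2, 7.8.2 | Visit 6 | 3.0 mmol/L or more |
| 6.9, 7.9 | Visit 7 | none |
| 5.1.1 | call between visits | 3.0 mmol/L or more |

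**Count.** Sections with the targeted question: 1 + 2 + 2 + 2 = 7. Naming 3.0: 7 of 7. Naming 1.5: 0 of 7. Visit 7 sections with a ketone item: 0 of 2. This counts wording; it is not a capture rate.

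**Reportable range (12.3.2).** Ketones of 1.5 mmol/L or more with provider contact, or 3.0 mmol/L or more regardless of contact. A level from 1.5 to below 3.0 is not reportable on its own.

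**Range left unprompted.** At Visits 3 to 6 this is 1.5 to below 3.0 mmol/L with provider contact. At Visit 7 no ketone level is prompted.

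**Example.** Ketones of 1.8 mmol/L with a call to a provider: 1.8 is at least 1.5, so the event is reportable; 1.8 is below 3.0, so the truthful answer to the ketone question is no.

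**Does the 1.5 criterion stand alone?** The list in 12.3.2 sits under a lead-in about DKA, which is loosely worded. But the preceding sentence asks for any one of four criteria, and 12.1.1 expressly covers ketosis without DKA. The stand-alone reading is the sound one.

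**Other routes to the same event.**

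- The open questions on adverse events, device effects and device issues, at Visits 3 to 7, set no threshold but name no ketone level.
- The item on glucose above 300 mg/dL, at Visits 3 to 7, would catch many episodes, but not ketosis with glucose at or below 300.
- The scheduled review of diabetes management and adverse events covers Visits 3 to 7, without stated ketone content.
- The request in 5.1.1 to call about any health-related issue is broad, but the ketone example it gives is again 3.0.
- No section names a download of the home ketone meter. Section 15.1 refers to device files in general, and participants may keep the meter at exit (6.8, 7.8).

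None of these names the band from 1.5 to below 3.0.

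**Recall period.** Visits 4, 5 and 6 each look back over a phase of at least 8 weeks, with real-time reporting encouraged. Visit 7 takes place only about 48 hours after home use of the equipment.

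**The case against.** The strongest reply is that the sections do not conflict. Section 12.3.2 defines what is reportable; the visit question is a supplementary prompt after an open question, and nothing obliges a prompt to list every criterion. Prompting at 3.0, the one level reportable on the number alone, is coherent. Device issues and device effects are also asked about at every visit, and 12.8 exempts an infusion set occlusion from device reporting only if it does not lead to ketosis, so the main pump mechanism has its own route. To be missed, an event would need ketones in the narrow band, a provider call, no facility care, no glucose above 300 mg/dL, no device issue reported, and no mention at any open question, review or call. If the provider contacted was the study team, the study already knows.

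Much of this stands. The residual gap is small, and the adverse event form and the training manual with the Glycemic Treatment Guidelines are not among the documents and may name 1.5 mmol/L. The absence of any mention of a meter download does not show that readings go unreviewed.

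It does not remove the point. The remaining routes rely on the participant recognising the episode as worth reporting, and the occlusion route does not help participants on injections, whom 3.5 admits. A prompt that already names one ketone criterion can cover the other at little cost.

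**Conclusion.** The concern holds. The targeted question leaves ketones of 1.5 to below 3.0 mmol/L with provider contact unprompted at Visits 3 to 6, and Visit 7 prompts no ketone level.

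The effect is limited. Most reportable events, especially DKA and those treated in a facility, should still surface by other routes. The practical gap is a provider call without facility care. Such an event is not DKA, which under 12.3.2 requires "Treatment provided in a health care facility", so it does not count toward the two-episode discontinuation rule in 12.11.1. The primary CV analysis is untouched. How many events would be missed cannot be derived.

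The conclusion rests on reading the 1.5 mmol/L criterion as sufficient by itself, and on the protocol text alone. Confidence is medium because the form and manual could already ask for the lower level. Even then, the protocol sections should agree. The change is worth making.

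**What to change.** At Visits 3 to 7, ask whether since the last visit the participant had ketones of 1.5 mmol/L or more, and whether there was any provider contact or facility care for acute hyperglycemia or ketosis. This replaces the ketone item in seven sections and adds one in 6.9 and 7.9. If the sponsor intends a different reporting level, amend 12.3.2 instead so that the definition and the questions match. The level at which participants should call the team (5.1.1) remains the sponsor's clinical decision.

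The cost is a slightly longer visit script, a few more recorded events, and wording changes in nine sections (7 + 2), which need IRB review and approval under 16.2.

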980 **7.1. Randomization to De-Escalation**

981 Eligible subjects will be randomized to therapy de-escalation (DSS→PF→SAM).

982 A baseline Hemoglobin A1C will be collected.

983 The participant will receive a mode change for Phase 1 according to the randomization scheme.

984 **7.2. Training on Phase 1 DiAs Mode**

985 Participants randomized to de-escalation will be trained to use DiAs in DSS mode, including the
986 following features:

- 987 • **Exercise Advice:** An advisory module that ensures safety of mild to moderate exercise by
988 predicting whether an exercise bout is likely to result in hypoglycemia and providing a
989 graded carbohydrate supplementation strategy and possible reduction in insulin advice.
- 990 • **Bedtime Advice:** Gauges overnight hypoglycemia risk and provides bedtime carbohydrate
991 advice.
- 992 • **Smart Bolus Calculator:** An advanced bolus calculator capable of accounting for several
993 factors such as exercise (activity on board), metabolic characteristics (correction based
994 on 45 min predicted glucose to account for insulin delays) and SI fluctuations (insulin
995 sensitivity tracker).
- 996 • **Treatment Parameter Optimization:** An optimization routine that analyzes the previous
997 30 days of CGM, insulin, and meal data to provide updated insulin treatment parameters
998 (CR, CF, and basal rate) to minimize glycemic risk.

999 **7.2.1. Phase 1 EMA Surveys**

1000 Over the course of 2-3 days every two weeks of Phase 2, the participant will be asked to complete
1001 a “Daily Diary” with 3-5 entries of 3-4 questions each day, for a minimum total of 48 entries per
1002 participant during each Phase.

1003 **7.2.2. Phase 1 Initiation Questionnaires**

1004 Participants randomized to de-escalation will complete the following questionnaires:

- 1005 • Pittsburgh Sleep Quality Index
- 1006 • Technology Expectations (burdens subscale only)
- 1007 • INSPIRE (revised for DSS)

1008 Once all training activities are completed, the participant will be given adequate supplies and
1009 study devices to last until the subsequent clinic visit. An appointment for Visit 4 will be scheduled.

CLINICAL PROTOCOL

1010 **7.3. Home Use of DiAs in Phase 1 Mode**

1011 The participant will complete a minimum of 8 weeks of DiAs use in Phase 1 Mode at home. During
1012 the course of Phase 1, participants will complete EMA surveys and post-phase questionnaires.

1013 **7.3.1. Phase 1 EMA Surveys**

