- 1050 • Diabetes Locus of Control

1051 **7.4.3. AE Assessment**

1052 The participant will be asked about any of adverse events, adverse device effects, and device
1053 issues since the last visit. The participant will also be asked if there were any low BGs <54 mg/dL,
1054 high BGs >300 mg/dL, or ketones ≥ 3.0 mmol/L since the last visit.

1055 Once all training activities are completed, the participant will be given adequate supplies and
1056 study devices to last until the subsequent clinic visit. An appointment for Visit 5 will be scheduled.

1057 **7.5. Home Use of DiAs in Phase 2 Mode**

1058 The participant will complete a minimum of 8 weeks of DiAs use in Phase 2 Mode at home.

1059 During the course of Phase 2, participants will complete EMA surveys and post-phase
1060 questionnaires.

1061 **7.5.1. Phase 2 EMA Surveys**

1062 Over the course of 2-3 days every two weeks of Phase 2, the participant will be asked to complete
1063 a “Daily Diary” with 3-5 entries of 3-4 questions each day, for a minimum total of 48 entries per
1064 participant during each Phase.

1065 **7.5.2. Post-Phase 2 Questionnaires Week 7**

1066 All participants will be sent the following questionnaires on week 7 (day 42 of Phase 2) and will
1067 be asked to complete them within 1 week:

- 1068 • Technology Acceptance (burdens subscale only)

CLINICAL PROTOCOL

1069 • Pittsburgh Sleep Quality Index

1070 • T1-Diabetes Distress Scale

1071 **7.5.3. Post-Phase 2 Questionnaires Week 8**

1072 All participants will be sent the following questionnaires on week 8 (day 49 of Phase 2) and will
1073 be asked to complete them within 1 week:

1074 • Hypoglycemia Fear Survey

1075 • Hyperglycemia Avoidance Scale

1076 • Confidence in Diabetes Self-Care Scale

1077 **7.6. Visit 5 – Phase 3 Initiation**

1078 The participant will begin Phase 3 according to the randomization scheme either via web
1079 conference or an office visit. The participant will remotely receive a mode change for Phase 3.
1080 Study staff will review the features of the Phase 3 system and answer any questions.

1081 **7.6.1. Training on Phase 3 DiAs Mode**

1082 Participants randomized to de-escalation will have any questions answered about resuming use
1083 of the DiAs system in SAM.

1084 **7.6.2. Phase 3 Initiation Questionnaires**

1085 Participants randomized to de-escalation will complete the following questionnaires:

1086 • INSPIRE (revised for DSS)

1087 • Diabetes Locus of Control

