1653 Sample size determination is based on our related pilot studies of DSS. We estimate that the
1654 effect size of DSS vs. SAM will be $f^2=0.22$. Power calculations (G*Power 3.1.9.2) assuming $\alpha=0.017$
1655 (corrected for multiple comparisons), 95% power, correlation of 0.55 between the repeated
1656 measures, and attrition of 20%, yield a sample size of N=100 subjects to be randomized at
1657 baseline, with N=80 subjects completing the study. PF vs. SAM assumes the same effect size. We
1658 expect that while overall DSS effect vs. PF will be smaller than vs. SAM, GV control over time will
1659 be more consistent. Aim 1.3 analysis therefore assumes a small effect size (0.15) but 5 repeated
1660 measures (bi-weekly) in each condition with higher correlation (0.65), leading to an achieved
1661 power of 97.2% for this Aim.

1662 **14.2.2. Exploration of the effect of treatment escalation vs. de-escalation:**

1663 A key advantage of the proposed study design (beyond the optimal statistical power) is the
1664 possibility to explore the glucose control and psycho-behavioral impact of features being added
1665 and/or enhanced with prescriptive components (DSS), vs. features being limited to information
1666 (PF) or even removed (SAM). We will perform this analysis by looking at the between factors in
1667 the repeated ANOVA analysis, contrasting the escalation group vs. de-escalation group. While

CLINICAL PROTOCOL

1668 not powered, this analysis will provide key insights in the future feature adaptation schemes
1669 based on the ATI.

1670 **14.3. Outcome Measures**

1671 **14.3.1. Glycemic outcomes:**

1672 The primary outcome of this study will be Glucose Variability (GV) as measured by CGM-based
1673 Coefficient of Variation (CV), as recommended by the International Consensus on Use of
1674 Continuous Glucose Monitoring. To further characterize glucose control, we will compute other
1675 CGM Consensus outcomes as well:

- 1676 • Average
- 1677 • Percent in different ranges:
 - 1678 ○ <50 mg/dL
 - 1679 ○ <54 mg/dL
 - 1680 ○ <60 mg/dL
 - 1681 ○ <70 mg/dL
 - 1682 ○ ≤70-≤180 mg/dL
 - 1683 ○ >180 mg/dL
 - 1684 ○ >250 mg/dL
 - 1685 ○ >300 mg/dL
- 1686 • SD and coefficient of variation
- 1687 • LBGI, HBGI, ADRR

1688 Each modality of treatment will be assessed using the last 4 weeks of CGM recordings, as we
1689 expect most of the GV benefits of each intervention to be realized within the first 4 weeks of the

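### Insulin settings updated under DSS may stay in force through PF and SAM in the de-escalation sequence, and the text plans no DSS-SAM estimate free of this carry-over

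*Combined protocol and SAP*

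**What the plan says.** Section 7.2 describes a DSS routine that analyses the previous "30 days of CGM, insulin, and meal data to provide updated insulin treatment parameters", listed there and in section 6.6.1 as CR, CF and basal rate. The module list in section 1.1.1 names only CR and ISF.

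Settings are entered at the training visit: pump settings in section 4.1.2 and DiAs settings before first use in section 4.1.3. Sections 7.4 and 7.6 describe a remote mode change, a review of features, questionnaires and an adverse event check. On the return to SAM, section 7.6.1 says only: "Participants randomized to de-escalation will have any questions answered about resuming use" of that mode. No section says which settings apply after DSS ends.

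There is no separate washout. Section 14.3.1 states: "Each modality of treatment will be assessed using the last 4 weeks of CGM recordings, as we", and then gives two reasons: most of the new mode's benefit should have appeared by week 4, and about 24 days of data suit the CV. Neither reason concerns the fading of the previous mode.

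Section 14.3.2 plans a repeated-measures ANOVA with order as a fixed factor. Section 14.4 adds an escalation versus de-escalation contrast, described as not powered.

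**The concern.** Superiority of DSS over SAM on CV is Aim 1.2, on the primary outcome. In escalation, SAM is observed before any DSS update. In de-escalation, SAM is observed after 8 weeks of DSS and 8 weeks of PF. A lead-in protects against effects that fade, but a changed carbohydrate ratio or basal rate stays until someone changes it.

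If updated settings persist and still help, SAM in one sequence is partly treated by DSS. The pooled contrast then averages two different quantities. A small or null DSS-SAM result could not be told apart from retained settings, and the text plans no estimate that would separate them.

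**Working it through.** **Inputs (section 14.2.1).** "effect size of DSS vs. SAM will be $f^2=0.22" as printed; "95% power, correlation of 0.55 between the repeated" measures; alpha 0.017; "baseline, with N=80 subjects completing the study". A 1:1 split of the sequences (40 and 40 completers) is an assumption, because the ratio is not stated.

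**Reproducing the plan's N.** Read 0.22 as Cohen's f, so d = 2 × 0.22 = 0.44 SD. Then dz = 0.44/√(2 × (1 - 0.55)) = 0.464. With 80 completers the noncentrality is 0.464 × √80 = 4.15, and two-sided power at 0.017 is 95.4%. The smallest N for 95% is 79, and 80/0.8 = 100 randomized, so the plan's figures reproduce. Reading 0.22 as f², as printed, needs only 20 completers, so f is used below.

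**Bias of the pooled contrast.** Let τ be the true DSS-SAM effect.
- Escalation: expected DSS - SAM = τ(1 + s).
- De-escalation: expected DSS - SAM = τ(1 - r).
- Equal-weight average = τ[1 + (s - r)/2].

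Period effects enter the two sequences with opposite sign and cancel in the average. An order main effect adds one constant to every phase of a sequence. It drops out of each within-person difference and leaves the average unchanged.

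**Power with s = 0** (dz × (1 - r/2), N = 80, alpha 0.017):

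| r | estimate / truth | power |
|---|---|---|
| 0 | 100% | 95% |
| 0.25 | 87.5% | 88% |
| 0.5 | 75% | 75% |
| 1 (extreme bound) | 50% | 36% |

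For scale, section 1.1.2 reports pilot CVs of 0.36 and 0.33, a difference of 3 points. At r = 0.5 that would be estimated as 3 × 0.75 = 2.25 points.

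**With s above zero.** r = 0.5 and s = 0.25 gives 1 + (0.25 - 0.5)/2 = 87.5% of the truth. r = s gives 100%. r = 0.25 and s = 0.5 gives 112.5%.

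**Would the planned checks show it?** A simulation used 3,000 trials per value of r, 40 per group, s = 0 and, as in section 14.2.1, a PF effect equal to that of DSS. At r = 0.25, 0.5 and 1 the mean estimate was 0.386, 0.327 and 0.219 SD against a true 0.44. At the 5% level the order main effect was significant in 6%, 7% and 12% of trials. The difference between sequences in DSS-SAM was significant in 9%, 18% and 53%. That difference has expectation τ(r + s) plus twice the Phase 3 minus Phase 1 period effect, so even a significant result would not identify carry-over.

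**A comparison free of carry-over.** In Phase 1, escalation is on SAM and de-escalation is on DSS, before any between-phase switch. Adjusting for run-in CV with correlation ρ, d = 0.44/√(1 - ρ²) and the noncentrality is d√(n/2). For ρ = 0.55 and n = 40 this is 0.527 × √20 = 2.36.

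| run-in ρ (assumed) | alpha | 40 per group | 50 per group |
|---|---|---|---|
| 0.55 | 0.017 | 47% | 58% |
| 0.55 | 0.05 | 64% | 74% |
| 0.3 | 0.017 | 36% | 45% |
| 0.3 | 0.05 | 53% | 63% |

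The lower ρ is shown because run-in can be as short as 14 days with 11 days of use (section 5.2.1), well below the 24 days the plan prefers for CV. The 50-per-group column assumes no loss during Phase 1.

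**The case against.** - **Persistence is not stated.** A reader might infer that the settings do carry over. The documents are silent, and the training manual was not available. The point is that the plan leaves persistence open and has no estimate protected against it.
- **Only part of DSS leaves anything behind.** Section 7.2 lists four modules. Exercise advice, bedtime advice and the bolus calculator end with the mode; only parameter optimization leaves settings. Section 1.1.1 also says parameters need periodic adjustment, and the SAM window opens 8 + 4 = 12 weeks after DSS ends, so the benefit may wane. Both points stand. They make r = 1 an extreme bound, so 36% power should not be read as the expected case.
- **The direction is not fixed.** A reader might infer that the DSS effect must be shrunk. PF gives weekly feedback, so learning carried from PF into escalation DSS is plausible. It could cancel the bias or reverse it.
- **Order is not ignored.** It is a fixed factor, and section 14.3.2 refers to Figure 4, which was not visible in the copy reviewed. The checks stand as checks, but they do not correct the estimate. The text calls all three Aim 1 analyses crossover analyses.
- **The Phase 1 comparison is weak.** A reader might set 36% beside 64-74% and conclude that Phase 1 is the stronger test. Those figures use different alphas. At 0.017 with 40 per group and ρ = 0.55, Phase 1 overtakes the crossover only above roughly r = 0.85.

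**Conclusion.** The concern holds as a gap in the plan: the settings in force after DSS are undefined, and the text describes no DSS-SAM estimate that is safe if they persist. The bias is (s - r)/2 of the DSS effect under 1:1 sequences. If s = 0 and a quarter to a half of the effect persists, the estimate is 87.5% to 75% of the truth and power is 88% to 75% instead of 95%. These figures rest on 0.22 being f, on the plan's correlation of 0.55, and on values of r and s that the documents do not supply. The documents do not support saying that the trial will miss a DSS effect, that the bias must run toward zero, or that a Phase 1 analysis should replace the crossover.

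**What to change.** 1. In section 14.3.2, pre-specify a supportive analysis that is always reported beside the crossover estimate: Phase 1 only, DSS versus SAM between the randomized groups, with run-in SAM CV as covariate. State that it is not powered.
2. Record the insulin parameters in force in each 4-week analysis window and tabulate them by phase and sequence, so that persistence can be seen.
3. Reconcile sections 1.1.1, 6.6.1 and 7.2 on which parameters are updated, and state in the visit sections which settings apply at each mode change. This review does not propose which.

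The cost is one model, one table and a short protocol clarification. The Phase 1 estimate will be less precise than the crossover estimate. Parameter history must also be captured if DiAs does not already store it; the server data that section 1.1.1 gives as examples do not include it.
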